#### **6.5 CONCOMITANT MEDICATIONS**

All concomitant prescription medications taken during study participation will be recorded on the appropriate study-specific data form. For this protocol, a prescription medication is defined as a medication that can be prescribed only by a properly authorized/licensed clinician. Medications to be reported on the data form and entered on the CRF are concomitant prescription medications, over-the-counter medications, and non-prescription medications.

### **7. ASSESSMENT OF SAFETY**

#### **7.1 SPECIFICATIONS OF SAFETY PARAMETERS**

### 7.1.1 DEFINITION OF AN EXPECTED TREATMENT EFFECT (ETE) AND AN ADVERSE EVENT (AE)

An expected treatment effect is defined as any typical treatment side-effect of the study devices of mild to moderate severity and lasting up to a typical maximum duration. An adverse event is defined as any new medical problem, or exacerbation of an existing problem, experienced by a participant while enrolled in the study, whether or not it is considered device-related by the investigator. All ETEs and AEs will be collected during the conduct of this trial.

### 7.1.2 DEFINITION OF SERIOUS ADVERSE EVENT (SAE)

Each adverse event should be assessed for its seriousness. The definition below should be used for this assessment. Please note that the term serious adverse event is not synonymous with a “severe” adverse event, which may be used to describe the intensity of an event experienced by the participant.

An adverse event should be classified as serious if it meets any of the following criteria:

- a. Death  
Death was an outcome of the adverse event.
- b. Life-threatening  
The participant was at substantial risk of dying at the time of the adverse event or use or continued use of the device.
- c. Hospitalization (initial or prolonged)  
Admission to the hospital or prolongation of hospitalization was a result of the adverse event.
- d. Disability or Permanent Damage  
The adverse event resulted in a substantial disruption of a person's ability to conduct normal life functions (ie, the adverse event resulted in a significant, persistent or permanent change, impairment, damage or disruption in the patient's body function/structure, physical activities and/or quality of life).
- e. Congenital Anomaly/Birth Defect  
Exposure to a medical product prior to conception or during pregnancy may have resulted in an adverse outcome in the child.
- f. Required Intervention to Prevent Permanent Impairment or Damage (Devices)  
Medical or surgical intervention was necessary to preclude permanent impairment of a body function, or prevent permanent damage to a body structure (either situation suspected to be due to the use of a medical product).
- g. Other Serious (Important Medical Events)  
The event does not fit the other outcomes, but the event may jeopardize the participant and may require medical or surgical intervention (treatment) to prevent one of the other outcomes.

Non-serious adverse events are all events that do not meet the criteria for a “serious” adverse event.

### 7.1.3 DEFINITION OF UNANTICIPATED ADVERSE DEVICE EFFECTS (EVENTS)

An unanticipated adverse device effect is defined as “any serious adverse effect on health or safety, or any life-threatening problem, or death caused by, or associated with, a device; if that effect, problem, or death was not previously identified in nature, severity, or degree of incidence in the investigational plan, or application (including supplementary application), or any other unanticipated serious problem associated with a device that relates to the rights, safety, or welfare of subjects.”

## 7.2 CLASSIFICATION OF AN EVENT

### 7.2.1 SEVERITY OF EVENT

Each adverse event should be assessed for its severity, or the intensity of an event experienced by the participant, using the following classifications:

1 = Mild	Discomfort noticed, but no disruption to daily activity
2 = Moderate	Discomfort sufficient that reduces or affects normal daily activity
3 = Severe	Inability to work or perform normal daily activity

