## 2.3 POTENTIAL RISKS AND BENEFITS

### 2.3.1 KNOWN POTENTIAL RISKS

This treatment modality was designed to inherently minimize the risk to the participant. As with any laser device treatment, there is a risk of adverse events, skin reactions or side effects. Expected side effects include:

- Discomfort: When a pulse is triggered, it may cause various degrees of discomfort. Some describe the sensation as stinging. A burning sensation may last for up to an hour after treatment.
- Blistering and burns
- Discoloration: Every laser treatment carries the possibility of permanent skin discoloration. Post-inflammatory hyperpigmentation and pigmentation are widely known complications of laser treatment.
- Eye injury: Protective glasses or goggles are provided for operators and assistants. It is extremely important to wear eye protection at all times during treatment to protect the eyes from accidental exposure to laser and serious injury.
- Infection: Every scar left on the skin carries the risk of infection. This risk of infection may also be associated with machines such as the MOSAIC ULTRA laser system. If detected, any infection should properly be treated with topical and/or systemic medications.
- Keloid formation: Scars may become thickened due to excessive growth of fibrous tissue.
- Prolonged redness: A mild case of temporary red spots is an expected reaction. However, if the red spots appear severe or last much longer than expected, do not repeat the treatment until the spots have disappeared. This reaction may vary by patient.

- Scarring: There is a possibility that scars may form due to treatment with the MOSAIC ULTRA laser system. Scars may form locally if treatment procedures are not properly followed, which may lead to exposure to laser, infection or physical irritation of the area such as wiping or rubbing.
- Delayed wound healing/skin textural changes: After laser treatment, the reepithelialization process may not proceed as expected due to the patient's physiological characteristics (e.g. lack of wound healing ability or poor care after treatment). This may result in undesirable changes to the skin texture.
- Temporary bruising

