#### 4.4 SUCCESS CRITERIA

The study will be considered a success if the following criteria are met:

Group A: Clinical Treatment Arm

1. Blinded evaluators are able to correctly identify the post-treatment image at least 80% of the time
2. The adverse event and side effect profile are acceptable

Group B: Biopsy Arm

1. Wounds induced by the treatment device appropriately healed as assessed by histology.

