### 6.3.5 POST-TREATMENT CARE

Participants will be advised:

- Do not use any scrubbing product for one week after treatment.
- Do not use functional cosmetics (eg, retinol, AHA) for 2 days.
- Avoid saunas for at least one week.
- Do not use cosmetic products (toner, lotion) containing alcohol. They may cause skin irritation. Use a mild moisturizer.
- Apply sun block cream (SPF 30, PA++) everyday, to prevent PIH. It is advisable to wear a hat and take an umbrella when going outside for 30 days after the procedure.
- Skin Dryness are normal reactions associated with the thermal effect, so please apply moisturizing cream frequently.

For subjects in Group B, post-biopsy instruction will be provided to the participant. The participant will be instructed to not fully submerge the biopsy site in water. The bandage or coverings for the biopsy site should be changed on a daily basis and should also be changed if it becomes wet or damp. The subject will also be told that once a scab or new skin begins to grow over the area and that the bleeding from the biopsy site has stopped they can discontinue the wound treatment regimen and remove the bandage.

Other post-treatment procedures will be considered and used as deemed by a clinician to be standard and reasonable care. Participants will be instructed that blistering, bleeding, oozing, strong pain, excessive swelling persisting for more than 48 hours, or signs of infection (eg, itching; pus; drainage; fever; chills) are cause for immediate concern.

There is a risk of an allergic reaction to the anesthetic or oral medication used in treatment and/or the biopsy. An allergic reaction to the anesthetic may cause: hives, itching, swelling, faintness, low blood pressure, difficulty breathing, and life-threatening shock. In the event of the aforementioned infection or allergic reaction scenarios, immediate emergencies (medically unstable) must be triaged in emergency care.

If the aforementioned side-effects are not an immediate emergency (medically stable), participants should contact the investigator and/or his designee, to be evaluated and potentially treated at no cost to the participant. An unscheduled visit will be arranged so that the Investigator can clinically evaluate and photograph these findings.

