### 7.2.3 EXPECTEDNESS

Reported events will be categorized as Expected Treatment Effects if the event meets the definition of any typical treatment side-effect of study devices of mild to moderate severity and lasting up to a typical maximum duration.

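### The severity scale cannot grade painless visible skin damage, and no stated durations back the rule that separates expected effects from adverse events

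*Combined protocol and SAP*

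**What the plan says.** Section 7.2.1 has three severity grades:

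- Mild: "Discomfort noticed, but no disruption to daily activity"
- Moderate: "Discomfort sufficient that reduces or affects normal daily activity"
- Severe: "Inability to work or perform normal daily activity"

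Section 7.1.1 defines an Expected Treatment Effect (ETE) as "any typical treatment side-effect of the study devices of mild to moderate severity and lasting up to a typical maximum duration". Section 7.2.3 repeats the rule: "Reported events will be categorized as Expected Treatment Effects if the event meets the definition of any typical treatment side-effect", with the same conditions on severity and duration.

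Section 2.3.1 lists ten items under a lead-in that calls them expected side effects. Four of them are or include discoloration, keloid formation, scarring and textural change of the skin. On the first it says: "Every laser treatment carries the possibility of permanent skin discoloration".

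Section 7.3 has ETEs and adverse events (AEs) both recorded, with severity, seriousness and resolution date. Changes in severity are documented so that an ETE can be reconsidered as an AE.

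Section 4.4 makes this one of Group A's two success criteria: "The adverse event and side effect profile are acceptable". Section 4.3.2 lists adverse event assessment as a secondary endpoint.

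**The concern.** In an aesthetic laser study the harm that matters most to a participant may be one that can be seen but not felt. The severity table has no place for how large, how visible or how lasting a skin change is. Section 9.3 summarises categorical data as counts and frequencies, so the grade and the ETE or AE label carry most of the information a reader of the safety summary will have. Section 4.4 sets no threshold for an acceptable profile, so that judgement will lean on those labels. If lasting marks appear as mild, or are graded differently at different sites because no grade fits, the profile will look better or less consistent than it was.

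**Working it through.** No arithmetic applies. The documents state no event rate, threshold or power for safety. The check applies the rules in turn to one case: a painless scar, keloid, or pigment or texture change that limits no daily activity.

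**1. Severity (7.2.1).**
- Severe needs inability to work or carry on normal activity: not met.
- Moderate needs discomfort that affects activity: not met.
- Mild needs discomfort to be noticed: read literally, not met either.

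The event therefore fits no grade. An investigator who must enter one will enter mild, since nothing higher is open. If the mark does stop the participant working, Severe becomes available, because that grade does not mention discomfort. The gap is confined to marks without functional effect.

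**2. ETE or AE (7.1.1, 7.2.3).** Three conditions must hold together.
- *Typical side effect.* The term is not defined. The lead-in to 2.3.1 gives some support for calling these harms expected.
- *Mild to moderate.* If the event is entered as mild, this is met. If it is left ungraded, it is not met. The scale's gap thus makes the ETE decision unstable as well.
- *Within a typical maximum duration.* A permanent mark should fail this. But the protocol text states no maximum for ETEs. In 2.3.1 only the burning sensation has a figure (up to an hour). Prolonged redness is described relative to expectation, without a number.

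**3. Re-categorization (7.3).** The only prompt named is a change in severity. A stable, painless mark shows none. Persistence is not excluded as a reason, but it is not named.

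**4. Seriousness (7.1.2).** Criterion d on disability or permanent damage does not depend on the severity grade. Its main clause concerns substantial disruption of normal life functions, and its explanatory wording extends to significant, persistent or permanent change in body structure or quality of life. A disfiguring scar could qualify; a small scar or pigment patch may not.

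**5. Establishing persistence (7.3 against 7.4.1).** Section 7.3 follows unresolved events at least every 7 days until they resolve or stabilize. Section 7.4.1 ends AE follow-up at the final study visit. On the second rule, a mark still present at that visit would be left without a known outcome.

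**The case against.** The strongest reply is that the definition already does its job: a permanent scar does not fall within a typical maximum duration, so filing it as an ETE would breach the protocol. Listing a harm as a known risk does not make it typical; 2.3.1 calls discoloration a possibility and ties local scarring to procedures not being properly followed. Seriousness gives a second route. ETEs are collected with resolution dates and regular follow-up, and the success criterion covers side effects as well as AEs, so an ETE label does not remove an event from that judgement. The operator manual and treatment guidelines (Appendices A and B) are attached documents not reproduced here and might list reactions and durations.

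Most of this stands. A reader might infer that the rules send painless permanent marks into the ETE category and out of safety reporting. The documents do not support that: the duration condition points the other way, both categories are recorded, and no separate AE table is defined from which events could vanish. A reader might also see a contradiction between 2.3.1, which lists blistering, burns and infection, and 6.3.5, which tells participants that "blistering, bleeding, oozing, strong pain, excessive swelling persisting for more than 48 hours, or signs of infection" call for immediate concern. That is not a contradiction, since a foreseeable risk can still need prompt evaluation.

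What the reply does not answer is the severity scale. Seriousness and severity are separate assessments, as 7.1.2 itself says, so criterion d cannot supply the missing grade. And a duration condition without durations cannot be applied alike at three sites.

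**Conclusion.** The concern holds in two parts of unequal weight.

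The firm part is that 7.2.1, followed exactly, cannot place a painless visible skin change above mild and literally gives it no grade. This touches four of the ten side effects named in 2.3.1.

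The weaker part is that misfiling a lasting mark as an ETE is possible, because the protocol text sets no maximum durations for ETEs and 7.3 names only severity change as a prompt. It would be an error against the definition, not a consequence of it.

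No count of affected participants can be given, because the documents state no rates for these harms. The conclusion assumes that the attached appendices do not supply a severity anchor or a list of durations; if they do, the second part shrinks to a missing cross-reference. The change should be made, since safety is both a secondary endpoint and a Group A success criterion.

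**What to change.** - **7.2.1:** add an anchor for the extent or visibility of skin change at each grade, and grade by the worse of that and activity impact.
- **Persistence:** record it as a separate item, for example present at the 90-day visit, yes or no. In Group B, whose last visit falls between days 19 and 90, record it at that visit with the day. Do not fold persistence into the grade: rating every mark still visible at day 90 above mild would mix duration with intensity and overgrade trivial residues.
- **7.1.1, 7.2.3 and 7.3:** limit ETEs to a named list of transient reactions, each with a stated maximum duration. State that an event outlasting its duration is re-categorized as an AE. State that scarring, keloid and persistent pigment or texture change are recorded as AEs.
- **7.3 and 7.4.1:** reconcile the two rules on following unresolved events. Which rule stands is for the sponsor and investigators to decide.

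The cost is an amendment to Section 7 and the adverse event form, with IRB approval. No visits are added, and photographs are already scheduled at the 30- and 90-day visits in Group A and at the biopsy visits in Group B. The downside is that reported AE counts and grades will look somewhat less favourable.

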### 7.2.2 RELATIONSHIP TO THE INVESTIGATIONAL DEVICE

The investigator should assess the relationship of the adverse event to the investigational device. The relationship should be assessed using the categories presented in **Table 5**.

**TABLE 2: RELATIONSHIP BETWEEN ADVERSE EVENTS AND INVESTIGATIONAL DEVICE**

Definite	Definite relationship exists between the device/procedure and an adverse event
Probably Related	A reasonable causal relationship between the device/procedure and an adverse event is more likely than not.
Possibly Related	A reasonable relationship exists between the device/procedure and an adverse event, but the causal relationship is unclear or lacking.
Not Likely Related	A temporal relationship exists between the device/procedure and an adverse event, but there is no reasonable causal relationship. For example the adverse event occurs in a time frame, which makes a causal relationship to device treatment improbable.
Unrelated	No relationship between treatment with the device/procedure and the adverse event exists.

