### 6.3.6 ELECTIVE SKIN BIOPSY

Some study-site locations may offer an elective skin biopsy for histological evaluations. The biopsy is considered a safe, low-risk procedure.

The biopsy procedure will involve collecting a small sample of skin from the participant in a discreet location. The punch biopsy, a tool that is usually circular at the extraction site, removes a small, round sample of the epidermis, dermis, and superficial fat (while leaving the extracted layers intact).

Prior to biopsy, participant skin will be cleaned and dried by the treating clinician. The punch instrument is pressed vertically into the skin and then rotated clockwise and counterclockwise between the fingertips. A small “give” can be felt as the device cuts through the epidermis and dermis, down to the superficial layer of subcutaneous fat. The punch biopsy tool is designed to collect tissue very quickly (to reduce pain) and is also designed to reduce the risks of bleeding through precision. However, some temporary pain and minor bleeding can occur at the biopsy site. The biopsy site will be covered with a bandage. There is a small risk of infection and participants must commit to taking care of biopsy site. Participants will be advised to regularly clean the biopsy site with mild soap and water, and to keep it bandaged (a simple bandaid is often enough) until it is fully healed (approximately one month).

For patients participating in the Group B of the study, the intended treatment area of the subject will be marked and photographed prior to treatment and a control biopsy will be taken. The first biopsy (Day 0, control) will be collected at this time. A normal treatment will be then be conducted using pre-determined laser parameters. Subject will then have a biopsy taken immediately post treatment from the treated area.

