## 7.3 TIME PERIOD AND FREQUENCY FOR EVENT ASSESSMENT AND FOLLOW-UP

The occurrence of an AE or SAE may come to the attention of study personnel during a study visit or upon review by a study monitor. All ETEs and AEs will be captured on the appropriate data form. Information to be collected includes event description, date of onset, clinician's assessment of seriousness and severity, relationship to study device/treatment (assessed only by those with the training and authority to make a determination), actions taken, and date of event resolution. All AEs occurring while on study must be documented appropriately regardless of relationship. All ETEs/AEs assessed as "not yet resolved" must continue to be followed via telephone contact, by email, or clinic visit every 7 days or sooner (as per the physician's direction until event resolution or stabilization or tissue resection).

A pre-existing condition should not be reported as an adverse event unless there has been a substantial increase in severity or frequency of the problem that has not been attributed to natural history.

Changes in the severity of an event will be documented to allow for a determination if the event should be re-categorized from an ETE to AE.

The PI will record all reportable events, with start dates, occurring any time after informed consent is obtained until seven days (for non-serious AEs) or 30 days (for SAEs) after the last day of study participation. At each study visit, the investigator will inquire about the occurrence of ETEs/AEs/SAEs since the last visit. Events will be followed for

outcome information until resolution or stabilization.

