## 9. STATISTICAL ANALYSIS

### 9.1 STATISTICAL AND ANALYTICAL PLANS

The primary analysis of efficacy will be by study group and will be based on the evaluable treated participants; hence, only those participants who received complete study treatments and completed a 30-day/90-day follow-up visit post-the-final-treatment-visit, and who have evaluable post-treatment images, will be included in the analysis. Analyses of safety will include all participants who received (complete or incomplete) study treatment.

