### 9.2 ANALYSIS DATASETS

The following analysis sets will be defined for the statistical analysis of this investigation:

Safety Evaluation Set (SES)

Subset of all participants who received the investigational treatment.

Full Analysis Set (FAS)

Subset of participants in SES that received complete treatments have primary effectiveness data available.

Per Protocol Set (PPS)

Subset of all participants who received complete treatments and have completed the study without major protocol deviations.

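### Biopsy events can be rated as device-related, because the causality scale merges device and procedure and no safety summary by group is specified

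*Combined protocol and SAP*

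**What the plan says.** Three places in the protocol describe the causality rating, and each names a different cause.

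- Section 7.2.2, instruction: "The investigator should assess the relationship of the adverse event to the investigational device".
- Section 7.2.2, relationship table: all five levels are worded for device and procedure together, for example "Definite relationship exists between the device/procedure and an adverse event".
- Section 7.3, items recorded for each event: "relationship to study device/treatment".

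The protocol does not define *procedure*. Section 5.3 (exclusion criteria) uses it for the laser treatment and Section 6.3.6 uses it for the biopsy. Section 6.3.6 also gives the biopsy its own expected events: "However, some temporary pain and minor bleeding can occur at the biopsy site". It names infection as well.

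On analysis, Section 9.1 states "The primary analysis of efficacy will be by study group". For safety it says only "Analyses of safety will include all participants who received (complete or incomplete) study treatment". Section 9.2 defines one safety set: "Subset of all participants who received the investigational treatment". The safety success criterion in Section 4.4 is listed under Group A and has no numerical threshold.

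**The concern.** Participants can undergo two interventions: the laser and a punch biopsy. Biopsy is required in Group B and optional in Group A. The objective is the safety of the laser, so the rating needs to say which intervention an event is attributed to. As worded, it may not.

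The two are hard to separate afterwards. Apart from the Group B control, biopsies in that arm are taken from laser-treated skin. The listed risks also overlap: infection appears for both the laser (Section 2.3.1) and the biopsy (Section 6.3.6). Expected Treatment Effects (Sections 7.1.1 and 7.2.3) are limited to typical side effects of the study devices. Expected biopsy pain or bleeding therefore has no category of its own and, if recorded as an adverse event, is rated on the merged scale.

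Error can run both ways. Biopsy wounds may raise the apparent device-related rate, or a laser injury may be put down to the punch. Attribution also bears on reporting, because the definition in Section 7.1.3 turns on harm associated with the device.

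**Working it through.** **Step 1. Number of biopsies.** The Synopsis gives 5 per Group B participant. Sections 6.3.6 and 6.4 reproduce this: 1 control + 1 immediately after treatment + 2 early follow-up + 1 final = 5. With up to 30 participants (Section 4.1) that is 30 × 5 = 150 biopsies, against 30 × 1 = 30 laser sessions (Section 6.3). Group B is 30/210 = 14.3% of the maximum treated population. The Group B schedule in Section 6.2 also marks a biopsy at the phone-call visit, which would make 6 each and 180 in all. Those places must be reconciled; 5 is used here.

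**Step 2. Clearest case.** The Group B control biopsy is taken before the laser treatment (Section 6.3.6). An event at that site cannot come from that treatment. If *procedure* includes the biopsy, the table allows it the highest level of relatedness. If the rater follows the instruction above the table, the same event is unrelated. Both readings are open.

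**Step 3. Possible size in the overall summary.** The documents give no event rates, so let r be an assumed event rate per biopsy, independent between biopsies.

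- Share of Group B with at least one biopsy event = 1 − (1 − r)^5
- Points added over 210 participants = 30 × [1 − (1 − r)^5] / 210

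| r (assumed) | Share of Group B | Participants | Points added, at most |
|---|---|---|---|
| 1% | 4.9% | 1.47 | 0.7 |
| 5% | 22.6% | 6.79 | 3.2 |
| 10% | 41.0% | 12.29 | 5.9 |

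These are upper figures for Group B's contribution at each r. They suppose that every biopsy event is rated related and that no affected participant also has a laser-related event. If 5% of participants have a laser-related event (assumed, independent of biopsy events), the points added are (30/210) × 0.95 × [1 − (1 − r)^5] = 0.7, 3.1 and 5.6. The pooled rate becomes 5.7%, 8.1% or 10.6% instead of 5.0%.

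**Step 4. Possible size in Group A.** Only optional biopsies enter here. With assumed uptake u, one biopsy per participant who accepts, and the same assumed 5% laser rate:

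- Group A rate = 0.05 + 0.95 × u × r
- u = 10%, r = 2%: 0.05 + 0.95 × 0.10 × 0.02 = 5.2%
- u = 25%, r = 5%: 0.05 + 0.95 × 0.25 × 0.05 = 6.2%

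The Group A schedule allows an optional biopsy at several visits, so more than one per participant would raise these figures.

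**The case against.** The strongest reply is that the scale can be read as concerning the laser only. The heading, the instruction and the table title in Section 7.2.2 name the investigational device, and two rows of the table speak of treatment with it. Taking a biopsy sample is not treatment with the device, so a punch-site bleed could properly be rated unrelated. This stands as far as it goes. A reader might infer that biopsy events *are* counted in the laser's safety profile, but the documents do not say so. They leave the word open, and the outcome may differ between raters and sites.

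A reader might also infer that Group B's 150 biopsies bear on the safety success criterion. They do not: Section 4.4 lists that criterion under Group A only. Nor does the criterion use a device-related rate or a threshold, so no shift computed here can be shown to change a success decision. Likewise, Section 9.1 defines who is in the safety analysis. It neither plans nor rules out tables by group, and no pooled rate over 210 participants is a stated endpoint.

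The plan does collect other information: "Information to be collected includes event description, date of onset, clinician's assessment of seriousness and severity". With group membership and photographs, this would separate many events. It would not reliably separate pain or infection in treated skin that has also been biopsied. The adverse event form is not in the documents, so the single causality item is inferred from Section 7.3.

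Finally, two ratings would not stop a laser injury from being attributed to the biopsy. That is correct, and it is why events related to both must stay in the device-related summary.

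**Conclusion.** The concern holds as an ambiguity with a cheap remedy, not as a demonstrated miscount. The cause being rated differs between the instruction, the scale and the recorded item, and neither a separate biopsy attribution nor a safety summary by group is specified.

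The effect would fall mainly on the overall safety summary: up to about 0.7, 3.2 or 5.9 percentage points over 210 participants at 1%, 5% or 10% per biopsy. Those rates are assumptions, as are independence between biopsies and the reading that rates every biopsy event as related. For Group A's criterion the effect is probably small, about 0.2 to 1.2 points in the illustration, and it rests on an uptake the plan does not state.

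This is a pilot with descriptive summaries (Section 9.3), so no test or sample size is affected. The change is still worth making before data are collected, because an attribution not recorded at the time may not be recoverable later.

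**What to change.** - **Sections 7.2.2 and 7.3:** replace the single rating with two on the same five levels, one for relationship to the laser device or treatment and one for relationship to the biopsy. Use the same terms in the instruction, the table and the list of recorded items. Record the anatomical site of each event, and whether it is a biopsy site.
- **Section 9.1:** tabulate safety by group and by biopsied or not (Group A without biopsy, Group A with biopsy, Group B). Base any device-related summary on events rated related to the laser, including those related to both, and list biopsy-only events separately.

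The cost is one or two extra form fields, one more table split and the matching protocol wording. Design, sample size and treatment do not change. Some events in biopsied, treated skin will remain hard to attribute.
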